**Alcohol craving scale**

We will use the Penn alcohol craving scale that has five items and is rated on a scale of 1 to 6.

**AUDIT-C**

The Alcohol Use Disorders Identification Test (AUDIT-C) is an alcohol screen that can help identify patients who are hazardous drinkers or have active alcohol use disorders (including alcohol abuse or dependence).

**Motor Threshold**

Motor threshold (MT) is defined as the TMS pulse amplitude needed to elicit an EMG response of 50  $\mu$ V peak-to-peak average amplitude in a target muscle. MT is the standard in the field for determining the intensity of TMS for everyone to reduce seizure risk. The MEP for the right first dorsal interosseous (FDI) will be measured with EMG. The scalp region producing the largest amplitude MEP will be identified. At that scalp location, we will determine the TMS intensity eliciting average MEP amplitude of 50  $\mu$ V peak-to- peak in the first DI muscle using an amplitude titration procedure (at least 5/10 trials). Individual MT will be used to determine the intensity of theta burst stimulation for everyone, as recommended by safety guidelines.

**cTBS application**

A magnetic coil will be placed on the scalp and held in place with frameless stereotaxic equipment, using a sophisticated method of coil placement that will coregister scalp positions directly onto an average brain template. This Frameless Stereotaxic System Brainsight offers real-time three-dimensional display of cortical localization as the TMS coil is moved across the scalp. This will be used for coil positioning. This system uses a programmed robot arm to precisely position the TMS coil, and maintain its position, within 1 mm of the brain target chosen. Earplugs will be worn to protect hearing and low-volume white noise will be played through TMScompatible headphones to mask the sound of the coil clicks. The intensity of the stimulation will be 120% of resting motor threshold as reported in a previous studies. The participant will be seated comfortably with headphones and earplugs to protect the subject's hearing. We will collect heart rate data on the second and third days of study using a Fitbit that will be strapped to the

participant's wrist.

## Attachments

Attach Type	File Name
ResearchProcedures	Purchase_Task.pdf
ResearchProcedures	AUDIT_C.pdf
ResearchProcedures	Penn_Alcohol_Craving_Scale_171.pdf
ResearchProcedures	Figure 1.png
ResearchProcedures	PreScrnF.pdf

## Data Collection & Research Materials

In this section, please provide the following:

- Describe all sources or methods for obtaining research materials about or from living individuals (such as specimens, records, surveys, interviews, participant observation, etc.), and explain why this information is needed to conduct the study.
- For each source or method described, please list or attach all data to be collected (such as genetic information, interview scripts, survey tools, data collection forms for existing data, etc.).
- If you will conduct a record or chart review, list the beginning and end dates of the records you will view.

Motor Threshold  
 Eye tracking  
 AUDIT- C  
 FTND  
 MAST  
 DAST  
 History if any of traumatic brain injury or loss of consciousness.  
 Alcohol craving scale  
 TMS Side effects scale  
 Treatment acceptability questionnaire (TAQ)  
 Resting state functional magnetic resonance imaging (fMRI)  
 Heart rate data using Fitbit

Neuroimaging data will be acquired on a Siemens 3-Tesla (3T) PRISMA scanner at the Magnetic Resonance Imaging and Spectroscopy Center (MRISC), situated close to Markey Cancer Center. A high-resolution (1 cubic millimeter voxels) T1- weighted MP-RAGE structural image will be acquired for each subject. Functional images will be acquired using echo-planar imaging. Hyper-angulated volumes will be acquired with 37 ascending and interleaved slices at an angle 30-degrees to the anterior-posterior commissure to prevent OFC washout. Additional parameters will be similar to those used in other approved neuroimaging protocols in our lab (e.g., a repetition time (TR) of 2 seconds, echo time (TE) of 25 ms, a flip angle of 90 degrees, and functional voxels of size 3.4mm x 3.4mm x 4.0mm). Image preprocessing will be performed in Conn Toolbox.

## Attachments

Attach Type	File Name
DataCollection	Demographics_TMSIRB86853.pdf
DataCollection	MAST.pdf
DataCollection	Fagerstrom_test.pdf
DataCollection	DAST-10-drug-abuse-screening-test.pdf
DataCollection	TMS Side effects.doc
DataCollection	Treatment acceptability questionnaire (TAQ).PNG

## Resources

Describe the availability of the resources and adequacy of the facilities that you will use to perform the research. Such resources may include:

- Staffing and personnel, in terms of availability, number, expertise, and experience;
- Computer or other technological resources, mobile or otherwise, required or created during the conduct of the research;
- Psychological, social, or medical services, including equipment needed to protect subjects, medical monitoring, ancillary care, or counseling or social support services that may be required because of research participation;
- Resources for communication with subjects, such as language translation/interpretation services.

The TMS Suite is housed within the department of psychiatry ([name]) at the University of Kentucky, Lexington. Currently it encompasses one experimental room covering about 600 sq feet on the second floor. We are in the process of purchasing a MagPro X100 stimulator (MagVenture Inc, Atlanta, GA) with booster option and active cooling. The room will also be equipped with a laptop and a chair to provide TMS. The device is capable of producing rTMS over a wide range of parameters such as paired-pulse, theta burst stimulation, and both monophasic and biphasic waveforms. The machine weighs 35 kg and the cart encompassing the machine weighs 16 kg. Dimensions of the machine are 210 x 530 x 400 mm. We are also in the process of purchasing a frameless stereotaxic system (Brainsight Frameless, Rogue Research, Montreal, QC, Canada) for

coregistration of TMS coil position on the scalp with underlying cortical anatomy on the individual subject's three-dimensional MRI scan. This permits navigation of the TMS coil to target cortical structures. Participants are administered TMS in a customized chair for stabilization of head and coil position. A coil holder especially designed for TMS ensures stable coil positioning. The Brainsight Neuronavigation system has three main components: (1) NDI Spectra infrared camera system, (2) stimulator, (3) chair with neck rest. The TMS coil is targeted to a user defined location selected on the individual 3-D Anatomical MRI with fMRI or PET data overlay with less than one millimeter error. The TMS coil is attached to a stimulator unit, which administers the TMS pulses to modulate brain function in a spatially and temporally precise fashion. The subject reclines in the chair and wears a headband equipped with a subject position tracker. The ceiling mounted infrared stereo camera detects the 3-D position of the subject tracker and also the coil position tracker, and continuously feeds this information into the control center software.

**Eye Tracker.** The Tobii Pro Fusion housed at [name] is an exceptionally flexible remote eye tracking system offering supreme tracking performance in a wide array of human behavior research studies. This small eye tracking research system offers unprecedented portability and freedom of head movement in combination with unparalleled tracking accuracy and robust participant tracking capability. It allows for both screen and real-world test scenarios. For screen based research, it can be used with a laptop, an external monitor or an all-in-one PC. It can be mounted below most screens. With the eye tracker flush mounted on a screen, researchers can achieve highly accurate results for stimuli presentation on screens. Using a desk stand, one can track larger screens. This gives researchers the freedom to present stimuli on a screen that best meets the specific needs of the study at hand. The eye tracking system captures data up to speeds of 250 Hz (available 60, 120, 250 Hz modes). It delivers unparalleled data accuracy within the whole tracking box and very robust participant tracking capability. Robust eye tracking capability ensures very low data loss in real life conditions. The system with automatic selection of bright or dark pupil eye tracking accommodates for large variations in experimental conditions and demographic populations. The system also comes fitted with Tobii Pro Lab. This is a versatile biometric software platform designed for extensive research into human behavior using eye tracking analysis. It also has added ability to be combined with other physiological data streams. From in-store shopper research to psychology experiments, Pro Lab makes it easy for anyone to start using various biometric tools in their research in order to further expand the scope and richness of their insights. Pro Lab works well with both screen-based and wearable eye trackers.

**Magnetic Resonance Imaging and Spectroscopy Center (MRISC).** The Magnetic Resonance Imaging and Spectroscopy Center (MRISC) is a service and consultation center supporting basic and clinical research at the University of Kentucky. The Center includes an advanced 3T Siemens PRISMA scanner with high performance gradients, echo-planar whole body imaging and hydrogen spectroscopic capabilities for both human and animal studies. For dedicated animal studies, a modern Bruker/Siemens 7T MR scanner has recently been installed. Recently renovated facilities for animal handling, preparation and care are available immediately adjacent to the 7T imager. There are also computing facilities, electronic and fabrication shops, and a multi-user laboratory available to support magnetic resonance and spectroscopy studies. Scientific and technical personnel are available to help in developing MR sequences and procedures as well as to help with image-processing analysis. The Center has multiple ongoing research trials <https://www.research.uky.edu/magnetic-resonance-imaging-and-spectroscopy-center/human-research-projects>. In 2017 the MRISC was awarded an NIH grant to upgrade its human MRI scanner from a Siemens TIM TRIO 3T to a Siemens MAGNETOM Prisma 3T. The Prisma 3T offers maximum performance under prolonged high-strain conditions and delivers improved resolution over the previous system by coils with the highest gradient strength currently available on the market. Of note, data collected with the Prisma 3T scanner are to a higher-quality standard and are therefore more attractive for inclusion into NIH-supported neuroimaging repositories, such as the Neuroimaging Informatics Tools and Resources Clearinghouse (NITRC) and the Human Connectome Project (HCP). The Prisma 3T is equipped with a full complement of coils, updated image processing using Siemens Software 3D rendering, image fusion, perfusion, DTI fiber tracking, spectroscopy, volume rendering, shaded surface display, multiplanar reconstruction, and maximum intensity projection.

**Ancillary Equipment in MRI Suite.** 1) Applied Sciences Laboratories, Inc. Model 504LRO (long range optics) eye tracker complete with Real Eye software; 2) AVOTEC, Inc. Silent Vision SL-6011 LCD projection system used with Psychology Software Tools, Inc. visual presentation software, EPRIME; 3) MRA, Inc. 10 channel, fiber optic, patient response system with trigger interface and visual/auditory patient monitoring; 4) Current Designs, Inc. patient response fORP Interface Unit with 12 fiber optic cables and an MRI compatible, handheld, trackball mouse; 5) Medrad, Inc. SHS200 Power Injector; 6) InVivo Research, Inc. Precess MRI compatible patient monitor, with wireless digital SPO2, ETC02, heart rate and blood pressure recording; 7) Full suite of physiological monitoring equipment from S.A. INC for small animal imaging; and 8) Microcapstar Capnograph CO2 Analyzer and MRI-1ventilator from CWE instruments for small and medium sized animals.

**Computing and Data Management.** The following centralized computer and file server equipment is located in the MRISC and available (1) Server, Linux, 4U Rack mounted Dell PowerEdge 6850, 64bit - 4 Quad Core Xeon Tulsa, 16GB RAM, 1.5TB SAS RAID 5 array; (2) Two Disk Array, 3U Rack mounted Dell MD1000 Power Vault, 4.5TB SAS RAID 5 array; (3) Tape Backup, 2U Rack mounted Dell TL2000, 24 x 800GB/1.6TB cartridges; (4) Network Attached Storage (NAS), 1U Rack mounted NetGear, 2.0 TB SATA RAID 5 array; (5) Dell full size 4210 rack (42U slots total; 16U slots occupied including APC; 26U slots available). All computers and servers are protected with power supply backup and surge protecting UPSs. All MRI scans are sent to the NAS backup server immediately after the imaging session and burned to CD for permanent archiving. The MRI scanner host computer is connected to the Dell rack, containing equipment items 1-4, by 1 GB/sec fiber optic cable while the rest of the computers are connected by Cat 5e cable on a 100 MB/sec network. Institution-wide upgrades to Cat 6a network cable are currently underway. Daily incremental tape backups are made from all data on all the servers, the NAS, and the MD1000 using Yosemite Backup software running on the Poweredge 6850. Full monthly tape backups are made and stored offsite. All computers and servers are behind the UK Medical Center firewalls, have individual firewalls, are accessible only with valid usernames and passwords, and have automated operating system software updating.

## Potential Risks & Benefits

### Risks

- Describe any potential risks – including physical, psychological, social, legal, ability to re-identify subjects, or other risks. Assess the seriousness and likelihood of each risk.
- Which risks may affect a subject's willingness to participate in the study?
- Describe likely adverse effects of drugs, biologics, devices or procedures participants may encounter while in the study.
- *Qualitative research* - describe ethical issues that could arise while conducting research in the field and strategies you may use to handle those situations.
- Describe any steps to mitigate these risks.

#### Benefits

- Describe potential direct benefits to study participants – including diagnostic or therapeutic, physical, psychological or emotional, learning benefits. This cannot include incentives or payments.
- State if there are no direct benefits.
- Describe potential benefits to society and/or general knowledge to be gained.

Describe why potential benefits are reasonable in relation to potential risks. If applicable, justify why risks to vulnerable subjects are reasonable to potential benefits.

#### Risks with TMS

Seizure is a theoretical risk with TMS. In the Rossi et al. report it was stated that "The occurrence of seizures has been extremely rare, with most of the few new cases receiving rTMS protocols exceeding previous guidelines, often in patients under treatment with drugs which potentially lowered the seizure threshold." As Rossi et al. delineate, "rare" means that 16 cases (out of tens of thousands of rTMS sessions over the last two decades) of seizure related to rTMS have been reported. Eight occurred before safety parameters were established in 1997. Of the other eight reports, six occurred either when the safe rTMS parameters were exceeded or other safety guidelines ignored, and the actual occurrence of a seizure has been questioned in the other two (i.e., convulsive syncope or pseudoseizure may have occurred). In a workshop convened by the National Institute for Neurological Disorders and Stroke (NINDS) in 1996, researchers in the field agreed upon a set of rTMS consensus safety guidelines, including recommended stimulation parameters and contra-indications, and these consensus guidelines have been recently updated (Rossi et al., 2009). Widespread adherence to the 1996 guidelines has resulted in the virtual elimination of inadvertent seizures in rTMS studies (Rossi et al., 2009). Theta burst stimulation (TBS) that we will use in this study has been documented to be extremely safe. The risk of seizure with TBS is 0.1% (Rachid, 2017). There has been only one seizure instance reported with continuous TBS in a subject with no previous history of epilepsy but was sleep deprived after a long flight (Oberman and Pascual-Leone, 2009).

The most commonly reported side effect of rTMS is headache. This headache is typically of a muscle-tension type. It usually develops during or immediately after the stimulation and may last for minutes to hours following the end of the stimulation. It is typically limited to the day of stimulation, and usually responds promptly to single doses of over the counter pain medications. Neck pain or scalp pain may also occur. Both are usually managed easily with over-the-counter analgesics.

As noted in Rossi et al. (2009), Loo and colleagues reported mild and transient changes in auditory threshold in two depressed patients following a 2-4 week rTMS course of rTMS (16). Cases of tinnitus have been reported after rTMS treatments. In addition, recently in a study investigating the effects of rTMS on symptoms of depression, a patient experienced moderate to severe tinnitus after an rTMS session in which earplugs were not used. Rossi et al. recommended that hearing protection always should be worn during rTMS application, and that individuals with cochlear implants not receive rTMS. In the current study, earplugs will be worn by all subjects during rTMS procedures. Individuals with cochlear implants will be excluded from participation.

Risks to the unborn children of pregnant women receiving rTMS are unknown. Pregnant women will be excluded in this study. If sexually active, the subject must agree to use appropriate contraceptive measures for the duration of the study. Medically acceptable contraceptives include: (1) surgical sterilization (such as a tubal ligation or hysterectomy), (2) approved hormonal contraceptives (such as birth control pills, patches, implants or injections), (3) barrier methods (such as a condom or diaphragm) used with spermicide, or (4) an intrauterine device (IUD). Contraceptive measures such as Plan B (TM), sold for emergency use after unprotected sex, are not acceptable methods for routine use. If the subject has any uncertainty about whether they could be pregnant, another urine pregnancy test will be performed before they can participate in this protocol.

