On day two of the study all study participants will receive active stimulation which is two sessions of continuous theta burst stimulation (cTBS) to the left dorsolateral prefrontal cortex. Both sessions will be separated by 50 minutes. Participants will perform the alcohol craving scale, AUDIT-C and attentional bias for alcohol cues before and after the two cTBS sessions. The same sequence of events will occur on day three of the study, but all participants will receive sham cTBS. We will acquire functional MRI (fMRI) scan on both study days 2 and 3, after the active cTBS sessions and sham cTBS session respectively. Study days 2 and 3 will be separated by a week.

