**Research Procedures**

Describe how the research will be conducted.

- What experience will study participants have?
- What will study participants be expected to do?
- How long will the study last?
- Outline the schedule and timing of study procedures.
- Provide visit-by-visit listing of all procedures that will take place.
- Identify all procedures that will be carried out with each group of participants.
- Describe deception and debrief procedures if deception is involved.

Differentiate between procedures that involve standard/routine clinical care and those that will be performed specifically for this research project. List medications that are explicitly forbidden or permitted during study participation.

On day one of the study, following informed consent, we will perform baseline assessments including breath alcohol level, alcohol craving questionnaire, alcohol attentional bias tasks using eye tracker, and collection of baseline demographics. All of these baseline assessments will take a total of three hours. We will evaluate for any contraindications for MRI using the MRI checklist (attached). We will also obtain resting and active motor threshold from the first dorsal interosseous (FDI) muscle. Following this subjects will be transported to Magnetic Resonance Imaging and Spectroscopy Center (MRISC), affiliated with University of Kentucky for collection of their baseline MRI brain scan that will last thirty minutes. A study team member will escort them to the MRISC and will be with them when the scan is obtained.

On the second day, subjects will receive two sessions of active cTBS. Sessions will be the same in dosing and will be delivered at an interval of fifty minutes. Each session will last five minutes regardless of it being cTBS or sham cTBS. Active cTBS sessions will be delivered 120% resting motor threshold (RMT) to the left dorsolateral prefrontal cortex using a figure 8 coil and MagVenture MagPro x100 device (MagVenture A/S, Denmark), with TMS coil position stabilized using BrainSight (Rogue Solutions, Montreal, Canada). Subjects will also perform a host of other tasks as shown in figure 1 before and after the two cTBS sessions. At the end of the cTBS sessions and tasks, post session MRI brain scan will be collected at MRISC.

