On day three of the study, participants will receive two sessions of sham cTBS. The sham cTBS mimics the actual experimental one but does not deliver any electricity to the brain. The sham sessions will be separated by 50 minutes. Participants will perform a host of other tasks as shown in figure 1 before and after the two sham cTBS sessions. At the end of day three, we will have participants undergo an MRI brain scan at MRISC.

A medical doctor will be present or nearby during all stimulation sessions. No drug, pregnancy, etc. screening results will be obtained from a UK HealthCare laboratory.

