#### Data and Safety Monitoring

The IRB requires review and approval of data and safety monitoring plans for greater than minimal risk research or NIH-funded/FDA-regulated clinical investigations.

- If you are conducting greater than minimal risk research, or your clinical investigation is NIH-funded, describe your Data and Safety Monitoring Plan (DSMP). [Click here for additional guidance on developing a Data and Safety Monitoring Plan](#).
- If this is a non-sponsored investigator-initiated protocol considered greater than minimal risk research, and if you are planning on using a Data and Safety Monitoring Board (DSMB) as part of your DSMP, [click here for additional guidance](#) for information to include with your IRB application.

We will monitor the safety of participants, i.e., potential adverse events resulting from participation; and have procedures to safeguard against adverse events. We will actively screen and exclude any potential participants with a history of seizure disorder. We will also monitor every study session with a physician on site for every stimulation session. In case a seizure were to occur, having a physician on site in the room with the participant will help us in managing the event. All staff will also be trained in how to provide first aid in the event of a seizure ie lay the participant on their side and move any objects that can cause harm out of their vicinity.

We will also monitor for side effects after every stimulation session including headaches and neck pain. We will actively exclude participants with metal implants or piercings so that no adverse events occur during the MRI scan.

We will assure data accuracy and protocol compliance, including quality-control procedures in place to assure data accuracy and completeness. Appropriate procedures range, for example, from regular data verification and protocol compliance checks performed by a data manager and a principal investigator, to a formal external data audit process by an external agent.

[Back to Top](#)

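### The readable plan describes side-effect checks only after stimulation, so symptoms present on arrival cannot be separated from new ones

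*Combined protocol and SAP*

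**What the plan says.** The one sentence that gives a time for side-effect checks is in Data and Safety Monitoring: "We will also monitor for side effects after every stimulation session including headaches and neck pain". Data Collection & Research Materials lists the "TMS Side effects scale" with no time points.

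For other measures the plan does name a value before stimulation. Study Design says of Day 2: "Participants will perform the alcohol craving scale, AUDIT-C and attentional bias for alcohol cues before and after the two cTBS sessions". It says the same sequence applies on Day 3 with sham. Research Procedures adds: "Subjects will also perform a host of other tasks as shown in figure 1 before and after the two cTBS sessions". Neither section names the side-effects scale, and neither do the Day 1 baseline lists.

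On spacing, Study Design says of the active day: "Both sessions will be separated by 50 minutes". Research Procedures says of the sham day: "The sham sessions will be separated by 50 minutes". On how long headache lasts, Risks with TMS says: "It usually develops during or immediately after the stimulation and may last for minutes to hours following the end of the stimulation". The same paragraph says headache is typically confined to the day of stimulation.

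Every participant has the active day first and the sham day a week later. The SAP covers craving (PACS) and attentional bias only. It has no rule for counting side effects or attributing them.

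**The concern.** Headache and neck pain, the effects the plan says it will look for, are common complaints that a participant may already have on arrival. A rating taken only after stimulation mixes those symptoms with new ones, and later analysis cannot separate them if no earlier score was taken. The plan gives its tested outcomes a same-day reference value but, in the readable text, gives none to its side-effect checks.

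The second question is which session a symptom belongs to. A headache that can last hours may be present at two ratings 50 minutes apart.

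What is at stake is the tolerability record. The Background section says that repeated cTBS sessions in one day, and cTBS to the left dlPFC, have not been studied before, so side-effect rates from even a small study are likely to be read with interest.

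**Working it through.** The documents state no side-effect rate, so there is no figure to reproduce. The calculation below uses assumed rates to show scale.

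**Inputs**
- Planned participants: 30 (Study Design). Enrolled: 8 (Subject Info To-Date).
- Sessions per stimulation day: 2 (Study Design, Research Procedures).
- *b*, share with the symptom on arrival: assumed 15%, range 5-30%.
- *i*, chance of a true new onset per session: assumed 20%.
- *q*, chance that a session-1 symptom lasts past 50 minutes: assumed 50%.
- Arrival symptoms are assumed to persist to a post-session rating and to be independent of new onset.

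**1. Arrival symptoms, participants affected per day**
- True share with a new symptom: 1 - (1 - i)² = 1 - 0.8² = 0.36.
- Share showing a symptom at any post-session rating: 1 - (1 - b)(1 - i)² = 1 - 0.85 × 0.64 = 0.456.
- Net excess: b(1 - i)² = 0.15 × 0.64 = 0.096.

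| b | Excess share | Of 30 | Of 8 |
|---|---|---|---|
| 5% | 0.05 × 0.64 = 0.032 | 1.0 | 0.3 |
| 15% | 0.096 | 2.9 | 0.8 |
| 30% | 0.30 × 0.64 = 0.192 | 5.8 | 1.5 |

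The result depends only moderately on *i*. At b = 15% the excess of 30 is 0.15 × 0.81 × 30 = 3.6 for i = 10%, and 0.15 × 0.49 × 30 = 2.2 for i = 30%.

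**2. How far the sham day helps**
- If *b* is equal on both days, the active-minus-sham difference shrinks by the factor (1 - b). With i = 30% active and 10% sham, the true difference is 0.51 - 0.19 = 0.32. At b = 15% it appears as 0.32 × 0.85 = 0.272.
- If *b* differs between visits, the order being fixed, the difference is biased and not just shrunk. With i = 20% on both days, so no true difference, and b = 15% on the active day against 5% on the sham day, the apparent difference is 0.64 × (0.95 - 0.85) = 0.064, or 1.9 of 30.

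**3. Symptoms left over from session 1**
- Among 30 people free of symptoms on arrival, true onsets number 30 × [i + (1 - iq)i] = 30 × (0.2 + 0.9 × 0.2) = 11.4.
- Symptomatic ratings number 30 × [i + 1 - (1 - iq)(1 - i)] = 30 × (0.2 + 1 - 0.9 × 0.8) = 14.4.
- A tally of ratings would exceed onsets by 3.0, or 26%. The number of participants affected per day is 30 × 0.36 = 10.8 whatever the value of *q*, so this excess arises only under a per-session tally.

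**The case against.** Four objections have force.

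- **Unseen material.** Figure 1 and the side-effects form are not shown, the scale is listed without time points, and the monitoring sentence does not exclude an earlier check. A reader might infer that no pre-session rating was ever taken. The documents do not support that; they show only that the readable text describes none.
- **Leftover headache.** A reader might infer that a headache left over from session 1 is wrongly blamed on stimulation. It is an effect of stimulation. Both sessions on a day are of the same type, and the plan expects such headache to end that day, so it moves neither to the other condition nor into the count of participants affected.
- **No counting rule.** A reader might infer that reported rates will be inflated by about a quarter. No section plans a per-session tally, so the 26% illustrates one possible way of counting and is not a forecast.
- **The sham day and importance.** The same monitoring applies on the sham day, which offsets stable background symptoms. Side effects are neither a stated objective nor a SAP outcome, and post-session checks serve participant safety as the plan intends.

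The last objection stands only in part. With sham always second, arrival symptoms that differ between visits do not cancel, and the SAP plans no active-versus-sham comparison of side effects. None of the four supplies a way to tell an arrival symptom from a new one.

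**Conclusion.** The point holds as a minor one. On the readable text, arrival symptoms cannot be separated from new ones, and the fixed-order sham day controls for this only in part. Under the assumed rates the net excess is about 2.9 (1.0-5.8) of the planned 30 participants per day, or about 0.8 (0.3-1.5) of the 8 enrolled. These figures scale with the assumed share symptomatic on arrival, for which the documents give no value.

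It would overstate the matter to count everyone who arrives with a symptom as an error (0.15 × 30 = 4.5, or 0.15 × 8 = 1.2), because some of them also develop a true new symptom that day. The 50-minute spacing affects only which session a symptom is assigned to. The craving and attentional-bias comparisons in the SAP are unaffected.

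**What to change.** In Data and Safety Monitoring and in the Day 2 and Day 3 procedures:

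1. Give the existing TMS Side effects scale once before the first session of the day, as well as after each session.
2. Count a symptom only if it is new, or worse than the previous rating that day.
3. Report the number of participants with any such symptom on the active day and on the sham day, not the number of session ratings. State this in the SAP.

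If Figure 1 or the form already schedules a pre-session rating, say so in the text and add only the counting and reporting rules.

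Progress of the Research says the study is closing with only data analyses left, so steps 1 and 2 help only further enrolment or a successor study. For participants who completed without a pre-session rating, report participants affected per day and state that arrival symptoms could not be separated.

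The cost is one more copy of a form already in use, a minute or two per visit, and a sentence each in the protocol and SAP. Asking beforehand may prompt slightly more symptom reporting on both days.
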